6. SAFETY ANALYSES

All safety analysis will be based on the Safety population. Descriptive summary will be based on nominal visits by treatment group and overall for double-blind period, and by treatment sequences and overall for on-vatiquinone period.

6.1. Duration of Treatment with Study Drug

Duration of treatment with study drug in double-blind phase will be calculated as number of days from the date of the first dose of double-blind study drug to the date of the last dose of the double-blind study drug, inclusive.

Duration of treatment with study drug in open-label period will be calculated similarly for open-label study drug.

In addition, total duration of vatiquinone will be calculated as number of the days from the date of the first dose of vatiquinone to the date of the last dose of vatiquinone, inclusive.

Duration of treatment will be summarized by treatment for double-blinded period for Safety Population, by treatment sequence for open-label period for Safety Populations, and for total duration for on-vatiquinone for Safety Population.

Duration of treatment will also be summarized by the following categories.

- Double-blind period
 - ≤28 days (≤4 weeks)
 - 29-56 days (4-8 weeks)
 - 57-84 days (8-12 weeks)
 - 85 – 112 days (12-16 weeks)
 - 113 – 140 days (16-20 weeks)
 - 141 – 168 days (20-24 weeks)
- Open-label period
 - every 84 days (12 weeks)
- On-vatiquinone period
 - every 84 days (12 weeks)

6.2. Adverse Events

The AE verbatim descriptions (investigator terms from the CRF) will be classified into medical terminology using the MedDRA. AEs will be coded by System Organ Class (SOC) and PT using MedDRA, Version 23.0 or later.

AE summaries will be presented by treatment for double-blind period, and by treatment sequence and overall for on-vatiquinone period, unless specified otherwise.

Only treatment-emergent AEs (TEAEs) will be included in summary tables. All AEs will be presented in subject data listings.

6.2.1. Treatment Emergent Adverse Event

A TEAE is defined as an AE that had an onset date on or after the first dose of study drug but prior to 30 days after last dose or it occurs prior to first dose of study drug and worsens in severity after first dose of study drug.

AEs with missing or partial onset date and cannot be determined if it occurred prior to the first dose of study or which treatment period it occurred will be counted as TEAE under that treatment period.

A TEAE will be considered occurring during double-blind period if the AE had an onset date or date of worsening on or after the date of first dose of double-blind treatment and:

- Prior to the date of the first dose of open-label treatment if subject enrolled into open-label period
- Within 30 days of the date of the last dose of double-blind treatment if the subject does not enroll into open-label period

A TEAE will be considered occurring during the on-vatiquinone period if the AE had an onset date or date of worsening on or after the date of the first dose of vatiquinone treatment and within 30 days of the date of the last dose of vatiquinone treatment.

Overview TEAE table, including number and percentage of subjects with TEAEs, treatment related TEAE, treatment related serious TEAEs, TEAEs leading to study discontinuation, TEAEs by severity, and treatment related AE by severity will be provided.

Summary information (the number and percentage of subjects by treatment group or by treatment sequence, where appropriate) will be tabulated for:

- Incidence of TEAEs by SOC and PT
- Incidence of TEAEs by PT in descending order
- Incidence of treatment-related TEAEs by SOC and PT
- Incidence of TEAEs by SOC, PT, and maximum CTCAE grade
- Incidence of TEAEs by SOC, PT, and relationship to study drug

AE tables will be sorted by SOC and then PT in decreasing frequency of the number and percentage of subjects in the Vatiquinone group.

By-subject listing will be provided for AEs.

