1.4.1. Nonclinical Safety Assessment Studies

Vatiquinone is an orally available compound that has been demonstrated in vitro and in vivo to cross the blood-brain-barrier. In 6-month (Study 1660-045) and 9-month (Study 1660-046) repeat-dose toxicity studies in rat and dog, respectively, the no observed adverse effect level (NOAEL) was 30 mg/kg/day, corresponding to Day 180 and Day 273 combined mean maximum observed plasma concentrations values of 8828 ng/mL (rat) and 12854 ng/mL (dog) and area under the plasma concentration-time curve from time zero to 24 hours values of 48,786 (rat) and

107,426 ng×h/mL (dog). The dose-limiting adverse effect in both rat and dog studies was anticoagulation as demonstrated by prolonged prothrombin time (PT) and activated partial thromboplastin time that most likely results from weak vitamin K antagonism exhibited by this class of compounds.

Vatiquinone was negative in the Good Laboratory Practice battery of genotoxicity assays including the bacterial reverse mutation Ames assay, the in vitro micronucleus assay in human peripheral blood lymphocytes, and the in vivo micronucleus assay in rats (Studies [AD75SX.503.BTL](#), [AD75SX.348ICH.BTL](#), and [AD75SX.125012ICH.BT](#)).

Safety pharmacology data collected in the 28-day toxicity studies in rat and dog and during the 6-month and 9-month toxicity studies in rat and dog, respectively, demonstrated that vatiquinone did not affect neurobehavioral or cardiovascular electrocardiogram (ECG) parameters (Studies [1660-027](#), [1660-028](#), [1660-045](#), and [1660-046](#)). In addition, vatiquinone is not a potent inhibitor of human ether-à-go-go-related gene channel current (Study [130416.FEK](#)). Vatiquinone did not influence respiratory function in rat (Study [1660-032](#)).

An in vitro phototoxicity study conducted in BALB/c 3T3 mouse fibroblasts (Study PTC743-2020-003) to assess phototoxic potential demonstrated that vatiquinone had no phototoxic potential when administered to the fibroblasts at concentrations up to 17,800 ng/mL (approximately 16 times the C_{max} obtained at the highest clinical dose of 400 mg).

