1.5. Risk/Benefit Assessment

1.5.1. Risk Assessment

At the dose levels selected for this study it is not foreseen that subjects will endure any risks greater than minimal. However, as the dose-limiting adverse effect in nonclinical toxicology studies was anticoagulation, to further minimize potential risks subjects will be frequently monitored for changes in coagulation parameters and other clinical pathology assessments. Administration of study drug will be adjusted or completely stopped if coagulation parameters (PT, partial thromboplastin time [PTT]) are found to be increased to more than 1.5×upper limit of normal (ULN).

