6. STUDY INTERVENTION DISCONTINUATION AND PARTICIPANT DISCONTINUATION/WITHDRAWAL

6.1. Discontinuation of Study Intervention

Subjects receive study treatment until treatment discontinuation for one of the reasons listed below. However, subjects may discontinue study treatment or withdraw their consent to participate in the study at any time without prejudice.

The following conditions require subject discontinuation from all study treatment:

1. At their own request or at the request of their legally authorized representative
2. If a subject experiences an AE that is deemed related to treatment with vatiquinone and, in the investigator's or the sponsor's medical judgment, continuation of treatment would be detrimental to the subject
3. Spontaneous bleeding in a subject
4. At the specific request of a regulatory agency for termination of treatment of an individual subject or all subjects under the protocol
5. Subject participation in another clinical study using an investigational agent or investigational medical device
6. Refusal of sexually active fertile subjects (excluding subjects who have been sterilized) to use medically accepted methods of contraception (Section [7.5.10](#))
7. If a subject becomes pregnant
8. Significant noncompliance with the protocol in the opinion of the investigator or the sponsor
9. Use of prohibited concomitant medication

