8.2. Sample Size Determination

It is planned to randomize 30 subjects per arm in this study. Sixty subjects (30 subjects in each treatment group) will provide a power of 81% to detect a 40% treatment difference with common standard deviation of 50% at a two-sided significance level of 0.05 based on the Wilcoxon Rank-Sum Test. The 40% treatment difference is based on 10% and 50% decrease in the placebo treatment group and PTC743 treatment group, respectively, for percent change from baseline in motor seizure frequency per 28 days.

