1.4. Sample Size Determination

It is planned to randomize 30 subjects per arm in this study. Sixty subjects (30 subjects in each treatment group) will provide 80% power to detect a 40% treatment difference with common standard deviation of 50% at a two-sided significance level of 0.05 based on the Wilcoxon Rank-Sum Test. The 40% treatment difference is based on 10% and 50% decrease in the placebo treatment group and vatiquinone treatment group, respectively, for percent change from baseline in motor seizure frequency per 28 days.

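### The SAP never counts subjects with any bleeding event by arm, so an excess spread over several coded terms is easily missed in the tables with 30 per arm

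*SAP*

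**What the plan says.** Protocol 1.4.1 states: "The dose-limiting adverse effect in both rat and dog studies was anticoagulation". It attributes this to weak vitamin K antagonism. Protocol 1.5.1 gives the same finding as the reason for frequent coagulation monitoring: "as the dose-limiting adverse effect in nonclinical toxicology studies was anticoagulation". Other sections follow from it. Section 4.3 excludes subjects whose screening INR is above normal, section 7.1.9 and Appendix 1 bar anticoagulants, section 7.4.6 has INR-triggered dose rules, and section 6.1 lists "Spontaneous bleeding in a subject" among the reasons for mandatory discontinuation.

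The human experience is described differently. Protocol 1.4.2 reports no coagulation changes deemed associated with vatiquinone in over 500 treated patients, and section 7.4.5 reports no dose-limiting toxicity in prior clinical studies.

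On the analysis side, SAP 6.2.1 plans an overview of all-TEAE totals and then tables such as "Incidence of TEAEs by SOC and PT", one of them by PT alone. SAP 6.2.2 (serious events and events leading to discontinuation) and 6.2.3 (exposure-adjusted rates) use the same SOC and PT rows, as does Protocol 8.4.6.4. SAP 6.3 counts subjects whose INR reaches one or 1.5 times the upper limit of normal. Neither document defines a bleeding group, a standardised query or an adverse event of special interest.

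**The concern.** Nosebleeds, bruising, gastrointestinal blood loss and blood in the urine would be coded to different PTs and, as a matter of general coding practice that the documents do not spell out, to different SOCs. An SOC total does not help, because it mixes bleeding with whatever else falls in that class. With 30 subjects per arm each bleeding row may hold only a few subjects.

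The randomised comparison is the best evidence this trial can give on whether the animal finding has a clinical counterpart, and no planned table presents it. A reader of the tables would have to find the terms, add them, and remove subjects counted twice. Terms grouped that way after unblinding are chosen with the results in view.

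**Working it through.** **The plan's own figures.** The documents give no number for bleeding. Their only power figure concerns the primary endpoint: the protocol says 60 subjects "will provide a power of 81% to detect a 40% treatment difference", and the SAP says "will provide 80% power to detect a 40% treatment difference", both with a "common standard deviation of 50% at a two-sided significance level of 0.05 based on the Wilcoxon Rank-Sum Test". Noether's formula has p = Φ(0.8/√2) = 0.714 and N = 60, so power = Φ(0.214 × √(12 × 60 × 0.25) − 1.96) = Φ(0.914) = 82.0%. A noncentral t calculation with the minimum Wilcoxon efficiency of 0.864 gives 80.6%. Both lie within 2 points of the stated values (a simulation with normal data gives 84.6%). This supports the design size, not any safety comparison.

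**Inputs for bleeding.** Arm size comes from SAP 1.4: "It is planned to randomize 30 subjects per arm in this study". Bleeding rates and the number of terms are not in the documents and are assumed below. No adverse-event test is planned, so p-values serve only as a yardstick for how visible a difference is.

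**One worked example.** Take 8/30 subjects with any bleeding on vatiquinone and 1/30 on placebo.
- Difference: 26.7% − 3.3% = 23.3 points. The Wilson limits are 14.2% to 44.5% and 0.6% to 16.7%, which give a Newcombe 95% interval of about 5 to 41 points.
- Fisher, two-sided: with 9 bleeders in 60, P(8 on active) = C(30,8)·C(30,1)/C(60,9) = 0.0119 and P(9) = 0.0010. Twice the unrounded sum is 0.026.
- Now split the same subjects over four PTs as 2 v 0, 2 v 0, 2 v 0 and 2 v 1, with nobody in two rows. For 2 v 0, p = 2 × 435/1770 = 0.49. For 2 v 1, p = 1.0.
- A single row against zero on placebo must reach 6 v 0 (p = 0.024) to fall below 0.05; 5 v 0 gives p = 0.052.

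**A range of assumed rates.** Let the any-bleeding rate P be split evenly and independently over k terms, so that the rate per term is 1 − (1 − P)^(1/k). The table gives the exact probability, with 30 per arm, that Fisher's test is below 0.05 with the excess on vatiquinone. It compares one grouped row with the chance that at least one of k separate rows gets there, 1 − (1 − f)^k, where f is the probability for a single row.

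| Any bleeding, placebo v active | Grouped row | Any of 4 rows | Any of 6 rows |
|---|---|---|---|
| 5% v 20% | 24% | 1.3% | 0.3% |
| 5% v 30% | 63% | 10% | 3% |
| 10% v 30% | 37% | 7% | 2% |
| 10% v 40% | 71% | 26% | 11% |

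For 5% v 20% and k = 4, the rate per term is 1.3% v 5.4%, or 0.38 v 1.63 expected subjects per row. Across the grid the active arm expects between 1.1 and 3.6 subjects per row.

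**Do other planned outputs give the count?**
- The INR table in SAP 6.3 counts laboratory values, not bleeds, and has no PTT threshold.
- Under Protocol 7.4.4, symptoms that accompany an abnormal laboratory value are reported as the event in its place, so the bleed and the value sit in different data sets. Both are listed, but no output pairs them.
- The discontinuation outputs in SAP 6.2.2 omit any bleed that did not lead to stopping.
- The event rate in SAP 6.2.3 counts repeated events of one type once, so recurrent bleeding does not show there.

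**The case against.** The strongest reply is that the data remain accessible. All adverse events are listed by subject. Serious events and those leading to discontinuation have their own listings and tables, INR elevations are counted at any post-baseline visit including unscheduled ones, and the DSMB sees unblinded safety outputs (SAP 3.3). In 60 subjects the bleeding terms can be found by hand. This stands. A reader might infer that a bleeding excess would be invisible; the documents do not support that. It would be unsummarised and easy to miss in the tables.

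Second, the hazard is nonclinical. A reader might infer that anticoagulation is the dose-limiting effect of the drug in patients, or that bleeding is the trial's main safety question. Protocol 1.4.2 and 7.4.5 report no such effect in people, and the stated safety objective in Protocol 2.1.2 is drug-related events and dose modifications. This also stands. It lowers the prior expectation but does not replace the placebo comparison.

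Third, the stop rule covers spontaneous bleeding only, so it should not be read as applying to every bleed. Spontaneous bleeds recorded as leading to discontinuation already have an output.

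Fourth, the 8 v 1 example is constructed, assumes no subject with two terms, and uses a test nobody will run. That is correct, and it is why the range above is given. Even the grouped row reaches only 24% or 37% in two of the four scenarios.

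Finally, the table specifications and the DSMB plan are separate documents and might contain a grouped display. That cannot be excluded, but neither document reviewed here commits to one.

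**Conclusion.** The point holds as a gap in presentation. The protocol treats anticoagulation as a risk to monitor, yet no planned table counts subjects with any bleeding event by arm. Under the assumed rates (5–10% on placebo, 20–40% on active, four to six terms), the chance that a nominal signal shows is 24–71% in one grouped row and about 0.3–26% in any separate row. These figures rest on rates and a split that the documents do not supply, and they describe visibility, not a planned inference. No data are lost, no bias arises and the primary analysis is unaffected. It is an inexpensive improvement that should be made, not a defect that undermines the trial.

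**What to change.** In SAP 6.2.1, fix a list of PTs for clinical bleeding (haemorrhage and bruising) before unblinding. Add one double-blind table for the Safety population giving, by arm, subjects with at least one bleeding TEAE (any, Grade 2 or higher, and leading to discontinuation), with the risk difference and exact 95% CI. Put TEAEs that report coagulation tests on a separate line. Pooling them would let a subject with only a prolonged test count as a bleeder, and INR elevation is already counted in SAP 6.3. Add a listing that sets each bleeding event beside the nearest INR and PTT. Repeat the table descriptively for the on-vatiquinone period. If unblinding has already happened, label the grouping as post hoc.

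The cost is one agreed term list, one table and one listing from data already collected. Treatment rules, the alpha allocation and the sample size do not change. The interval will still be wide for a small excess and should be reported as such.

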6.2.2. Deaths, serious AE, and AE leading to discontinuation

The following summaries will be presented:

- Incidence of treatment-emergent SAEs by SOC and PT
- Incidence of treatment-related, treatment-emergent SAEs by SOC and PT
- TEAEs leading to discontinuation by SOC and PT

Subjects who die, who have SAE and AE leading to discontinuation during the study will be listed in three separate listings.

6.2.3. Exposure Adjusted TEAE

The exposure-adjusted TEAEs will be summarized by treatment and by treatment sequences during on-vatiquinone for safety population as follows:

- Number of subjects and incidence rate per patient-years TEAE by SOC and PT
- Number of events and event rate per patient-years TEAE by SOC and PT

For incidence rate, subjects will be counted only once for a particular event. For event rate, repeated events of a particular type will be counted only once. Total patient years of exposure will be calculated as total duration in days divided by 365.25 days.

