8.4.6.4. Adverse Events

Summary information (the number and percent of subjects by treatment) will be tabulated for:

- Treatment-emergent adverse events (TEAEs)
- Treatment-related AEs
- TEAEs by severity
- SAEs
- AEs leading to discontinuation

Summaries will be presented by treatment groups and categorized by System Organ Class and Preferred Term. The frequencies of AEs displayed will be the crude rates that represent the number of subjects experiencing AEs divided by the total number of subjects.

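### The exposure-adjusted event rate in SAP 6.2.3 ignores repeats: in PT rows it duplicates the incidence rate, and recurrent non-seizure AEs are missing from the planned AE summary tables

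*SAP*

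**What the plan says.** SAP 6.2.3 (Exposure Adjusted TEAE) lists two outputs. The first is "Number of subjects and incidence rate per patient-years TEAE by SOC and PT". The second is "Number of events and event rate per patient-years TEAE by SOC and PT".

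The counting rules follow. For the first output: "For incidence rate, subjects will be counted only once for a particular event". For the second: "For event rate, repeated events of a particular type will be counted only once". One denominator is defined for both: "Total patient years of exposure will be calculated as total duration in days divided by 365.25 days". No censoring of exposure at first event is described. The section does not define *type*, and it does not say whether repeats are collapsed within a subject.

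The other AE tables are subject-level. SAP 6.2.1 introduces its list with "Summary information (the number and percentage of subjects by treatment group or by treatment sequence, where appropriate) will be tabulated for". SAP 6.2.2 plans incidence tables for SAEs and discontinuations. Protocol 8.4.6.4 describes AE frequencies as "crude rates that represent the number of subjects experiencing AEs divided by the total number of subjects". Individual events are kept in listings; SAP 6.2 says "All AEs will be presented in subject data listings".

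**The concern.** An event rate is normally reported beside an incidence rate because it answers a different question. The incidence rate says how many subjects are ever affected per unit of exposure; the event rate says how often the event happens. Here both have in effect the same numerator rule and the same denominator, so the second output adds nothing in PT rows and its label is wrong.

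The event rate is also the only planned AE table that could show recurrence. The protocol treats frequency as a safety matter: under 7.5.1 a preexisting condition becomes an AE when its episodes become more frequent, and under 7.5.3 a higher frequency can make an event unexpected. If vatiquinone raised the number of episodes of, say, vomiting or infection in subjects who would have had at least one anyway, the AE tables for the two arms could look alike.

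**Working it through.** The documents state no AE rate, so there is no figure to reproduce. The check applies the counting rules as written.

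**Inputs from the documents.** 30 subjects per arm (SAP 1.4); 168 days of double-blind treatment (SAP 5.1.1); division by 365.25 (SAP 6.2.3). One fully followed arm gives 30 × 168 / 365.25 = 13.80 patient-years (kept unrounded below).

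**Assumptions, for illustration only.** Six subjects have PT A, with k episodes each. Three of the six also have PT B once, in the same SOC.

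**Formulas.**
- Incidence rate = distinct subjects / patient-years.
- Event rate under the SAP rule = distinct subject-by-type pairs / patient-years.
- Event rate with all episodes = episodes / patient-years.

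**PT row (PT A), per patient-year.**

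| k | Incidence rate | Event rate, SAP rule | Event rate, all episodes | Understatement, 1 − 1/k |
|---|---|---|---|---|
| 1 | 6/13.80 = 0.435 | 0.435 | 6/13.80 = 0.435 | 0% |
| 2 | 0.435 | 0.435 | 12/13.80 = 0.870 | 50% |
| 3 | 0.435 | 0.435 | 18/13.80 = 1.304 | 67% |
| 5 | 0.435 | 0.435 | 30/13.80 = 2.174 | 80% |

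Within one PT, the number of distinct subject-by-PT pairs is the number of affected subjects. The second and third columns are therefore equal for any data set, not just this one. The understatement depends only on the mean number of episodes per affected subject: neither arm size nor exposure enters it.

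**SOC row, per patient-year.** The incidence rate is 6/13.80 = 0.435.
- If *type* means PT, the SAP event rate is (6 + 3)/13.80 = 0.652. It exceeds the incidence rate because two PTs are added, and it stays at 0.652 for every k.
- If *type* means SOC, the SAP event rate is 0.435, again for every k.
- Counting all episodes, (6k + 3)/13.80, gives 0.652, 1.087, 1.522 and 2.392 for k = 1, 2, 3 and 5.

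Under either reading the SAP event rate is flat in k, while the all-episode rate rises.

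**The per-subject reading.** The sentence does not say that repeats are collapsed within a subject. The parallel incidence rule suggests it. The other literal reading, one event per type for a whole treatment group, would not give a usable rate.

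**Is recurrence counted elsewhere?** For seizures, yes: all motor seizures on valid diary days (SAP 5.1.1), status epilepticus occurrences (5.2.1.2), total seizures (5.2.2.1), rescue medication uses (5.2.2.4) and motor seizure clusters (5.2.2.5). Disease-related hospitalization days (5.2.1.1), and disease-related emergency room visits and admissions (5.2.2.3), are also counted. Recurrent non-seizure AEs that do not lead to such a visit or admission are counted in no planned table.

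**The case against.** Five objections deserve weight.

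- *Recurrences are not lost.* This stands. Every AE goes into by-subject listings, onset dates are recorded (Protocol 7.5.5), and the DSMB reviews unblinded safety outputs (SAP 3.3; Protocol 9.1.5). A reader might infer that recurrent toxicity cannot be seen at all; the documents do not support that. What is missing is an aggregate count by treatment, which a listing does not supply.
- *The two rates are not always equal.* This stands for SOC rows if *type* means PT. Equality is certain only in PT rows.
- *Seizure worsening would still show.* This stands. Seizure recurrence is counted in the efficacy summaries, so it is not an example of a hidden signal. The same holds in part for infections or vomiting that lead to a disease-related admission or emergency room visit.
- *The size is not known.* This stands. Quoting 67% alone would amount to assuming three episodes per affected subject. Protocol 7.1.7 expects many disease-associated AEs but says nothing about how often they recur.
- *The table may not compare vatiquinone with placebo.* SAP 6.2.3 refers to treatment and to treatment sequences during the on-vatiquinone period, and can be read as covering that period only. There would then be no concurrent placebo column, and the double-blind patient-years used above would be the wrong setting. The identity in PT rows and the 1 − 1/k result hold under either scope.

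The sentence may be a slip for counting each event every time. That is plausible, but it does not help: the text states the opposite, and a programmer who follows it will produce a mislabelled table. The table shells are in a separate document that is not available here.

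**Conclusion.** The rule is wrong as written. Read per subject, it makes the PT-level event rate a copy of the incidence rate, and it contradicts the label of its own output. At SOC level the event rate does not respond to repeats under either meaning of *type*. Repeat episodes of non-seizure AEs are thus absent from every planned AE summary table.

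The PT event rate is understated by 1 − 1/k, from 0% at k = 1 to 80% at k = 5. Here k is the mean number of episodes per affected subject, and it is an assumption. A reader might infer that all reported AE rates are too low. They are not: the incidence rate and the crude percentages properly count each subject once. Nor does the point touch the primary analysis, type I error, power or sample size. It is a fault in descriptive safety reporting, worth correcting because correction is nearly free.

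**What to change.** Replace the event-rate sentence in SAP 6.2.3 with: *For event rate, every TEAE episode (each distinct onset), including repeated events in the same subject, will be counted, at both PT and SOC level.* Keep the once-per-subject rule for the incidence rate only.

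This wording removes the undefined term *type*. Because it counts by onset, a change in severity within one episode does not become a second event. That agrees with Protocol 7.5.7, which records the highest grade for each episode. The same edit should state whether the table covers the double-blind period, the on-vatiquinone period or both.

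The cost is one sentence in the SAP and one change to the counting step in the program. No new data are needed, since onset dates are already collected.

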3.2. Study Duration and Number of Sites

3.2.1. Duration of Subject Treatment

The maximum duration of subject treatment will be approximately 72 weeks (including placebo-controlled phase and extension phase). The overall study duration will be a maximum of approximately 78 weeks per subject.

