2.2.2. On-vatiquinone Period

On-vatiquinone period is defined as the period from the first dose of vatiquinone, regardless of double-blind or open-label vatiquinone, to the end of the study.

On-vatiquinone period will be used for summarizing safety endpoints.

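### The exposure-adjusted incidence rate counts each subject once but keeps dosing time after the first event in the denominator, which dilutes the rate for common terms and does so unequally between treatment sequences (minor)

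*SAP*

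**What the plan says.** SAP 6.2.3 plans two exposure-adjusted rates by SOC and preferred term (PT): subjects with an event per patient-year, and events per patient-year. On the first numerator it says: "For incidence rate, subjects will be counted only once for a particular event". On the second: "For event rate, repeated events of a particular type will be counted only once". One denominator serves both: "Total patient years of exposure will be calculated as total duration in days divided by 365.25 days".

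SAP 6.1 supplies the meaning of duration: "total duration of vatiquinone will be calculated as number of the days from the date of the first dose of vatiquinone", up to and including the last vatiquinone dose.

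The rates are to be "summarized by treatment and by treatment sequences during on-vatiquinone for safety population". SAP 2.2.2 defines the on-vatiquinone period as "the period from the first dose of vatiquinone, regardless of double-blind or open-label vatiquinone", running to the end of the study. Its length therefore depends on sequence. Protocol 3.2.1 states: "The maximum duration of subject treatment will be approximately 72 weeks". That is the planned exposure of a completer on vatiquinone/vatiquinone. A completer on placebo/vatiquinone receives only the 48-week extension (Protocol 3.1.4).

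For the on-vatiquinone period, SAP 6.2.1 accepts a treatment-emergent event that starts or worsens in this window: "on or after the date of the first dose of vatiquinone treatment and within 30 days of the date of the last dose".

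**The concern.** The purpose of dividing by exposure is to make groups with unequal treatment time comparable. In an incidence rate, a subject who has had the first event of a term can add nothing more to the numerator. If that subject's later dosing time stays in the denominator, the rate falls as exposure lengthens, even when the underlying hazard is constant. The longer-treated sequence then shows the lower rate for that reason alone, and both rates lie below the true first-event rate.

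The event rate beside it does not repair this. It also counts repeats of a type once, so the section contains no undiluted figure.

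There is a second, smaller mismatch. Events are accepted for 30 days after the last dose, but duration stops at the last dose.

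**Working it through.** The documents give no adverse event rate, so there is no planned figure to reproduce. The check asks what the rule returns when the hazard is known.

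**Inputs from the documents**
- Vatiquinone/vatiquinone completer: 72 weeks = 504 days; 504/365.25 = 1.380 years.
- Placebo/vatiquinone completer: 48 weeks = 336 days; 336/365.25 = 0.920 years.
- Double-blind period: 24 weeks = 168 days; 168/365.25 = 0.460 years.

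**Assumption.** The hazard of a first event, L, is constant and equal in both sequences, and nobody drops out. It is indexed by p, the risk of a first event within 24 weeks, so L = -ln(1-p)/0.460. The range for p is 2% to 50%.

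**Rule as written.** Expected rate = (1 - exp(-L×T))/T. Since 48 and 72 weeks are two and three times 24 weeks, this is (1-(1-p)^2)/0.920 for the shorter sequence and (1-(1-p)^3)/1.380 for the longer.

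Worked line, p = 20%:
- True rate: 0.2231/0.460 = 0.485 per year.
- 72 weeks: 0.488/1.380 = 0.354.
- 48 weeks: 0.360/0.920 = 0.391.
- Ratio: 0.354/0.391 = 0.90.

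Rates per 100 patient-years:

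| 24-week risk | True | Rule, 72 weeks | Rule, 48 weeks | Ratio |
|---|---|---|---|---|
| 2% | 4.4 | 4.3 | 4.3 | 0.99 |
| 5% | 11.2 | 10.3 | 10.6 | 0.975 |
| 10% | 22.9 | 19.6 | 20.7 | 0.95 |
| 20% | 48.5 | 35.4 | 39.1 | 0.90 |
| 50% | 150.7 | 63.4 | 81.5 | 0.78 |

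The correct ratio is 1.00 in every row. If every subject has the event, the ratio tends to 48/72 = 0.667.

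**Time stopped at first onset.** Simulating 200,000 subjects per sequence and dividing by time to first event (or T if none) gives ratios of 0.99, 1.01 and 1.00 at 5%, 20% and 50%. The rates are about 11, 49 and 150 per 100 patient-years in both sequences, which match the true values.

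**Post-dose window.** Letting the numerator run 30 days past the last dose gives (1 - exp(-L×(T+30/365.25)))/T. The extra window is 30/504 = 6% of the longer duration and 30/336 = 9% of the shorter. It raises both rates, so it partly offsets the dilution in level. It raises the shorter sequence more, so the ratios fall to 0.95, 0.88 and 0.76 at 5%, 20% and 50%.

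**Shorter open-label exposure.** With only 12 or 24 weeks of open-label treatment (36 or 48 weeks in total on vatiquinone/vatiquinone), the ratio is 0.975 at 5%, 0.90 at 20%, and 0.74 or 0.75 at 50%.

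**Double-blind arms.** Both have T = 24 weeks. If the reference risk is p and the true hazard ratio is 2, the rule gives (1-(1-p)^2)/p = 2 - p. That is 1.95, 1.80 and 1.50 at 5%, 20% and 50%.

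**The case against.** The strongest reply is that this is a supplementary descriptive table. No test or decision rests on comparing the two sequences, both of which receive vatiquinone, and inference is confined to the double-blind period (SAP 3.2). Crude incidence by SOC and PT, serious event tables and listings (SAP 6.2.1 and 6.2.2) show subject counts without this denominator. A reader might infer that common toxicities would be hidden, or that vatiquinone would look safer than placebo through unequal exposure. The documents support neither: the crude tables remain, and the randomised arms have the same planned duration.

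The full 72- against 48-week contrast also needs completed extension data. SAP 1 says this plan covers the double-blind period and leaves the open-label period to a separate SAP. That limits the point but does not remove it, because this SAP does specify the on-vatiquinone summaries and the rule.

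SAP 6.2.3 says only total duration, and SAP 6.1 defines a total duration for vatiquinone alone. Reading it as whole dosing time joins the two sections. Nothing in the SAP suggests a stop at first onset.

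Chance variation is also large. With the planned 30 per arm all completing, expected subjects with the event at 20% risk are 30×0.488 = 14.6 and 30×0.360 = 10.8. The standard error of the log ratio is √(0.512/14.64 + 0.640/10.8) = 0.31, a 95% factor of exp(1.96×0.307) = 1.83 either way, which swamps a bias of 0.90. At 50% the counts are 26.25 and 22.5, the standard error is √(0.125/26.25 + 0.25/22.5) = 0.126 and the factor is 1.28, about the same size as the bias (1/0.78 = 1.28). So the reply stands for moderate frequencies and is weaker for very common rows.

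Finally, a reader might infer that numerator and denominator disagree at both ends. They do not: both start at first dose and differ only after the last dose.

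**Conclusion.** The point holds and is minor. As written, the incidence rate understates common terms and SOC rows. At a 24-week risk of 20% it returns 73% of the true rate over 72 weeks (35.4/48.5) and 81% over 48 weeks (39.1/48.5). The spurious sequence ratio is about 0.90 at 20% and 0.78 at 50%. At 2% to 10% it is 0.95 to 0.99, which is of little consequence.

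These sizes rest on an assumed constant hazard, equal in both sequences, and on completers. Events concentrated early would push the ratio towards 0.667, and a hazard that rises with time could offset the effect. If the same rate is tabulated for the double-blind arms, there is no artefact from unequal planned duration, but a true ratio is shrunk towards 1 for common events. Primary and key secondary efficacy, alpha and sample size are unaffected.

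**What to change.** In SAP 6.2.3, and carried into the open-label SAP, define the incidence-rate denominator for each SOC or PT row as the sum over subjects of time at risk. It starts at the first dose of the period. It ends at first onset (or qualifying worsening) of that term or, if there is none, at the end of the treatment-emergent window, cut at first open-label dose, last contact or death as applicable. This also removes the post-dose mismatch from the incidence rate.

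Keep total exposure as the event-rate denominator. Extending that one to 30 days after the last dose would be a preference, and the documents do not require it.

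The cost is a few lines of SAP text and a per-term at-risk time in the adverse event programming. It needs no data beyond dosing, onset and contact dates already collected.
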